# **Caffeine supplementation improves the cognitive abilities and shooting performance of trained e-sports players**

## **Project summary**

We explored the effect of 3 mg/kg of caffeine supplementation on the cognitive ability and shooting performance of trained e-sports players. We recruited nine e-sports players who had received professional training in e-sports and had won at least eighth place in national-level e-sports shooting competitions. After performing three to five familiarization tests, we employed a randomized crossover design to divide participants into a caffeine trial (CAF) and a placebo trial (PL). The CAF group took capsules with 3 mg/kg of caffeine, whereas the PL group took a placebo capsule. After a 1-h rest, the Stroop task, visual search ability test, and the shooting ability test were conducted.

## **Introduction**

Owing to the popularity of e-sports, numerous countries have recognized e-sports as a formal sport. E-sports were also included as a demonstration event at the 2018 Asian Games in Jakarta. Professional e-sports leagues have been founded in several countries. E-sports include multiplayer online battle field arena games (e.g., *League of Legends*), first-person shooter games (e.g., *Counter-Strike: Global Offensive*, and *Valorant*), real-time strategy games, and sports games (1). Studies on first-person shooters have revealed that players with experience in competitions had shorter reaction times in a Stroop test (2) and stronger visual search abilities (3). Therefore, improving cognitive abilities that relate to e-sports competitions may be critical for participants in first-person shooter competitions, and external nutrients that enhance cognitive abilities may be crucial to their success.

Caffeine is a popular and effective ergogenic supplementation for athletes of all levels (4, 5). It is typically consumed through food and drink, and the mechanism through which low-dose caffeine acts as a psychostimulant is based on central antagonism at the A1 and A2A adenosine receptors. The capacity of caffeine to bind adenosine receptors facilitates the inhibition of the brake that endogenous adenosine imposes on the ascending dopamine and arousal systems, which facilitates cholinergic and dopaminergic transmission (6, 7). Therefore, caffeine consumption may improve energy, mood, cognitive function, attention, simple reaction time, choice reaction time, and memory and alleviate fatigue (8, 9). The consumption of caffeine 1 hour before playing a first-person shooter can improve players' visual search ability and speed in a state of alertness (10). A dosage of 3 mg/kg of caffeine before a game can increase

players' typing speed (11), shorten their reaction times, and increase their shooting accuracy (12). However, few studies have explored this.

Because visual search ability and the presence of decoys, which can distract players, can both affect play performance in first-person shooters, reaction time alone is insufficient as an index for cognitive ability in research on the effect of caffeine on shooting accuracy. We explored the effect of caffeine ingested 1 hour before a first-person shooter on players' performance by using a Stroop task and testing the players' visual search and shooting abilities.

## **Methods**

### **Participants**

We recruited nine healthy male adults (with the desired age and training). All participants had experience with national competitions and regularly underwent training in first-person shooters. They consumed less than 80 mg of caffeine a day and did not have any diseases affecting the heart, bones, and joints or diseases that preclude exercise. Before the experiment, all participants were fully informed of the experimental procedures and the possible risks, and they provided informed consent. This study received approval from the Institutional Review Board of Jen-Ai Hospital – Dali Branch (110-06). This study was conducted in accordance with the Declaration of Helsinki.

### **Design**

We adopted a randomized crossover design and divided the participants into a caffeine trial (CAF) and placebo trial (PL). The order of the trials in a test was randomized, and tests were separated by 7 days to avoid interference. At least 1 week before the formal experiment, all participants participated in three to five familiarization tests, such as cognitive function tests and shooting tests. The primary outcome was cognitive function, and the secondary outcome was shooting performance.

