### **Outcome measure**

The color–word Stroop task and visual search test were conducted using Psych/Lab for Windows. Measures used in the literature with satisfactory reliability and validity were adopted. The Stroop task involved four base colors, namely red, green, blue, and yellow, and the names of the base colors were presented in Chinese characters and in various colors to confuse the participants. The participants were required to press a key corresponding to the base color name they saw on screen (“R” for red, “G” for green, “B” for blue, and “Y” for yellow). In each test, 80 trials lasting 5 min each were conducted. The test results comprised a congruent condition, in which the key pressed corresponded correctly to the color on screen, and an incongruent condition, in which the key pressed corresponded incorrectly to the color name on screen.

In the visual search test, participants identified orange “T”s on the screen from upside-down orange “T”s, blue “T”s, and upside-down blue “T”s. When an orange “T” would appear, the participants were required to press the space bar as quickly as possible. If no orange “T” appeared, the participants were required to not react. A total of 80 search displays were presented in 5 min. In each display, 5, 10, 15, or 20 -Ts were presented.

The shooting ability test involved a three-dimensional aim trainer, which was proposed in a previous study [12]. Participants used the mouse to shoot the electronic targets on the computer screen. The test comprised 60 targets and could be completed in 2 min. It was performed on a static map with medium difficulty. In each round, three targets appeared at once, and participants were required to shoot them within 2 s, ideally eliminating each target with a one-shot kill. Participants’ kill ratio (number of targets

hit/60), hit accuracy (60/number of shooting), and average time to target were noted.

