### **Statistics**

All data are presented as averages  $\pm$  standard deviations. The Shapiro–Wilk test was used to examine the normality of the data. Cognitive performance, accuracy, and hit reaction time were analyzed through a paired sample t test. We used G\*power 3 software to achieve an alpha value of 5% and a power of 0.8; a sample of six was considered sufficient for this study. All data were calculated using SPSS (version 20, Chicago, IL, USA), and the significance level was  $\alpha < 0.05$ .

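### The primary outcome is named only as a domain, so the 5% alpha and 0.8 power belong to no stated score, and the Stroop conditions are defined by the key pressed instead of the stimulus

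*Protocol*

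**What the plan says.** The Design section of the protocol fixes the hierarchy: "The primary outcome was cognitive function, and the secondary outcome was shooting performance".

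The Outcome measure section describes two cognitive tasks.

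- **Stroop task.** The instruction is: "The participants were required to press a key corresponding to the base color name they saw on screen". Two results are reported. The first is "a congruent condition, in which the key pressed corresponded correctly to the color on screen". For the second, the wording turns from the colour to its name: "an incongruent condition, in which the key pressed corresponded incorrectly to the color name on screen".
- **Visual search test.** Set size varies: "In each display, 5, 10, 15, or 20 -Ts were presented". Participants respond when the target is present and withhold a response when it is absent.

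Neither task is given a score such as response time, proportion correct, interference difference or search slope. The same section does name the scores of the secondary outcome: a kill ratio, a hit accuracy and a mean time to target.

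The Statistics section says: "Cognitive performance, accuracy, and hit reaction time were analyzed through a paired sample t test". It sets alpha at 5% and power at 0.8, and concludes that "a sample of six was considered sufficient for this study". It gives no variable, effect size or standard deviation for that figure. The Participants section reports the number enrolled: "We recruited nine healthy male adults".

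**The concern.** Alpha and power are properties of one test of one variable. Here the variable is left open between two tasks, two Stroop conditions, four set sizes and more than one possible metric. Response time cannot be assumed as the default, because the Introduction argues that response time by itself is not an adequate index of cognition in this setting. Several cognitive results could each be presented as the primary one, and nothing in the protocol prevents the choice from being made after the data are seen.

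The Stroop wording is a second, separate defect. In a Stroop task, congruency describes the stimulus: the word either matches or does not match the colour in which it is shown. The protocol attaches the labels to the response instead. Followed as written, the rule would not yield performance on conflicting stimuli.

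**Working it through.** **1. The plan's own figure.** Inputs from Statistics: alpha 0.05, power 0.8, n = 6, paired t test. Sidedness is not stated, so two-sided is assumed. No effect size is given, so n = 6 cannot be reproduced, only solved backwards. With dz the mean paired difference divided by its standard deviation,

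power = P(|T| > t₁₋α/₂, n−1), where T is noncentral t with n − 1 degrees of freedom and noncentrality dz·√n.

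- n = 6, power 0.80: dz = 1.43 (1.19 if one-sided).
- The same dz at the nine recruited: power 96%.
- n = 9, power 0.80: dz = 1.07.

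The value 1.43 is the only one tied to the protocol's stated n and power, but it is back-solved and refers to no identified score.

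**2. What leaving the variable open could cost.** The protocol states neither the number of measures nor the rule for success, so both are assumptions. Suppose k cognitive measures are each tested at two-sided 0.05, there is no caffeine effect, and any one significant result counts. With independent measures the false-positive rate is 1 − 0.95^k:

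- k = 2: 1 − 0.9025 = 9.75%
- k = 3: 1 − 0.8574 = 14.3%

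Measures on the same person are likely to be correlated, which lowers these rates. Simulation of nine paired differences (200,000 trials per cell, equal correlations) gives:

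| Measures | Correlation 0 | 0.5 | 0.9 |
|---|---|---|---|
| 2 | 9.8% | 9.1% | 7.3% |
| 3 | 14.2% | 13.0% | 8.8% |

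If instead all three had to be significant, there would be no inflation: the rate runs from 2.0% at correlation 0.9 to under 0.1% at 0.

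**3. The Stroop definitions, taken literally.** Read the colour on screen as the display colour. The instructed key is the one for the colour name.

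| Stimulus | Key pressed | Meets the congruent definition | Meets the incongruent definition |
|---|---|---|---|
| Word matches display colour | Correct key | yes | no |
| Word matches display colour | Any other key | no | yes |
| Word differs from display colour | Name key (as instructed) | no | no |
| Word differs from display colour | Display-colour key | yes | yes |
| Word differs from display colour | Any other key | no | yes |

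Every trial labelled incongruent is an error against the instruction. A correct response to a conflicting stimulus, which is the response of interest, falls in neither class. If the colour on screen is read as the colour name, the two labels become simply correct and incorrect. On either reading they do not separate matching from conflicting stimuli.

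**4. Power under a multiplicity rule (n = 9, two-sided).**

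| Rule | dz 1.43 | dz 1.07 |
|---|---|---|
| One named variable at 0.05 | 96% | 80% |
| Holm, 3 measures, only one with an effect | about 87% | about 59% |

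For two co-primaries, a plain split to 0.025 each gives 91% at dz 1.43. Holm is never less powerful than that split.

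**The case against.** Several objections have weight.

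- **Scoring detail and multiplicity often sit in a SAP, and none is shown.** This stands for how scores are derived and adjusted. It does not cover the primary outcome itself, which the protocol fixes at domain level and to which it attaches alpha, power and a sample size.
- **The error rates depend on a success rule that the protocol does not state.** This stands. A reader might count six cells (two Stroop conditions plus four set sizes) and quote 1 − 0.95⁶ = 26.5%. The documents do not say that each cell is tested separately, or that one success is enough.
- **The intended Stroop design is probably the usual one.** The protocol says that colour names were shown in varying colours so as to mislead, so conflict was built into the stimuli. This makes the definitions a likely drafting error and means no loss of data is shown. The stated rule still gives the wrong quantity if followed.
- **The correct key is given.** A reader might infer that it is unsettled because one definition refers to the colour and the other to the colour name. That goes too far: the instruction is to press for the colour name. The definitions need to be aligned with it.
- **A single response-time primary would clash with the Introduction.** This stands, and it is why two co-primaries are offered below.

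**Conclusion.** The point holds in two parts. First, no cognitive score is designated as primary, so the stated 5% and 0.8 attach to no identifiable test, and the supporting result can be selected afterwards. Under an assumed any-one-counts rule with nine participants, this would raise the false-positive rate from 5% to about 7-10% for two measures or 9-14% for three. Second, the Stroop conditions are defined by the response and need rewording whatever a SAP may contain.

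A reader might infer that six or nine participants are too few. The documents do not support that: with no effect size given, adequacy cannot be judged either way, and at the effect implied by the plan's own n and power, nine participants give about 96% for a single variable. Nor do the documents show that a result was in fact selected after the event; they only leave that open. This should be corrected, and it is cheap to do so.

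**What to change.** 1. **Outcome measure.** Define congruent and incongruent by whether the colour word matches its display colour. Score correctness in both conditions against the instructed target. State the score taken from each task.
2. **Design.** Name the primary variable by task, condition and metric. Alternatively, given the Introduction's view of response time, name one Stroop score and one visual search score as co-primaries, with Holm or a fixed test order. Claim an effect only for those that pass, and make the other cognitive measures secondary.
3. **Statistics.** Tie alpha, power and sample size to the named variable or variables, and state the assumed effect size.
4. **If outcome data have already been examined** (the text is in the past tense), naming a variable now does not restore 5%. Apply Holm across all cognitive measures or label the cognitive results exploratory.

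**Cost.** If the data are unexamined, this means wording in three sections and fewer measures able to support the primary claim. One named variable loses no power. With Holm the loss is modest at the effect implied by the plan (96% to about 87% with three measures and one true effect), but larger if the true effect is smaller (80% to 59% at dz 1.07). A fixed order keeps the full 0.05 for its first test but stops at the first failure. If the data have been examined, the cost is a weaker or exploratory claim.

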### **Experimental procedure**

All tests were conducted in a professional e-sports classroom, and the indoor ambient temperature was set at 26°C. Participants' diet and meal times were recorded for the 3 days before the first experiment, and the participants were required to follow the same diet 3 days before the subsequent experiment. They were also required to

avoid food and beverages with caffeine (e.g., coffee, energy drinks, chocolate, and tea) during this period.

On the day of the formal experiment, participants had breakfast and lunch at 8:00 a.m. and 12:00 p.m., respectively, and arrived at the classroom at approximately 3:00 p.m. for the experiment. The participants took capsules with 3 mg/kg of caffeine (the CAFtrial) or a placebo capsule (the PLtrial) with 200 mL of water. The placebo capsule contained flour. Each participant had a computer with a frame rate of at least 240 Hz and a mouse of scrolling speed of 1 ms. After the participants remained in the room for 1 hour, during which they were required to take a rest in any form of their choosing except engaging in esports, the Stroop task, visual search test, and shooting ability test were conducted.

### **Outcome measure**

The color–word Stroop task and visual search test were conducted using Psych/Lab for Windows. Measures used in the literature with satisfactory reliability and validity were adopted. The Stroop task involved four base colors, namely red, green, blue, and yellow, and the names of the base colors were presented in Chinese characters and in various colors to confuse the participants. The participants were required to press a key corresponding to the base color name they saw on screen (“R” for red, “G” for green, “B” for blue, and “Y” for yellow). In each test, 80 trials lasting 5 min each were conducted. The test results comprised a congruent condition, in which the key pressed corresponded correctly to the color on screen, and an incongruent condition, in which the key pressed corresponded incorrectly to the color name on screen.

In the visual search test, participants identified orange “T”s on the screen from upside-down orange “T”s, blue “T”s, and upside-down blue “T”s. When an orange “T” would appear, the participants were required to press the space bar as quickly as possible. If no orange “T” appeared, the participants were required to not react. A total of 80 search displays were presented in 5 min. In each display, 5, 10, 15, or 20 -Ts were presented.

The shooting ability test involved a three-dimensional aim trainer, which was proposed in a previous study [12]. Participants used the mouse to shoot the electronic targets on the computer screen. The test comprised 60 targets and could be completed in 2 min. It was performed on a static map with medium difficulty. In each round, three targets appeared at once, and participants were required to shoot them within 2 s, ideally eliminating each target with a one-shot kill. Participants’ kill ratio (number of targets

hit/60), hit accuracy (60/number of shooting), and average time to target were noted.

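### The Stroop response rule points to the written colour name while scoring refers to both colour and name; followed literally, the task is word-directed and creates less of the conflict it is meant to create

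*Protocol*

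**What the plan says.** The Outcome measure section of the protocol describes four base colours and says that "the names of the base colors were presented in Chinese characters and in various colors to confuse the participants". The response rule follows: "The participants were required to press a key corresponding to the base color name they saw on screen", with the keys R, G, B and Y. No sentence tells players to respond to the print colour or to ignore the meaning of the character.

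The results are then split in two. One part is described as "a congruent condition, in which the key pressed corresponded correctly to the color on screen". The other part is described by a different reference: "an incongruent condition, in which the key pressed corresponded incorrectly to the color name on screen".

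The Introduction explains why more than speed is measured. It refers to "the presence of decoys, which can distract players, can both affect play performance in first-person shooters" and concludes that "reaction time alone is insufficient as an index for cognitive ability". The Stroop task, the visual search test and the shooting test are then named together as the measures. The Design section makes cognitive function the primary outcome.

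**The concern.** In a colour-word Stroop task the player reports the print colour and has to hold back the reading of the word. The conflict comes from the word intruding on the colour response. The instruction in this protocol reverses the roles: the word is what the player must report, and the print colour is what has to be ignored. Reading a word is ordinarily the more practised response, so a mismatched print colour should disturb it less.

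The consequence is one of interpretation. The Introduction wants something beyond reaction time. If players respond to the word, the Stroop score moves towards a choice reaction time, and a faster score under caffeine is weaker evidence of better handling of distraction. A null result would likewise say less about it. Because the scoring sentence uses a different reference in each half, a reader cannot tell from the protocol which task was intended.

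**Working it through.** The point turns on wording, so the check sets the statements side by side and applies them to concrete stimuli.

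**1. Which dimension each statement uses (Protocol, Outcome measure)**

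| Statement | Reference |
|---|---|
| Stimulus | written name, with print colour varied to confuse |
| Response rule | name |
| Congruent condition | colour on screen |
| Incongruent condition | colour name on screen |

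In the stimulus sentence, names are the written characters and colours are the print colours. Carried into the next sentence, the rule asks for the word.

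**2. Applying the statements literally**

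| Stimulus | Key | Right under the response rule? | Congruent (key matches colour)? | Incongruent (key does not match name)? |
|---|---|---|---|---|
| Word red, printed red | R | yes | yes | no |
| Word red, printed red | B | no | no | yes |
| Word red, printed blue | R | yes | no | no |
| Word red, printed blue | B | no | yes | yes |
| Word red, printed blue | G | no | no | yes |

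On a mismatched stimulus, the response that obeys the rule falls in neither condition, and the response that follows the print colour falls in both. The three statements cannot all be meant literally.

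**3. Reading both scoring references the same way**

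If colour and colour name both mean the word, or both mean the print colour, the two conditions become correct and wrong key presses. Neither reading separates trials by whether word and print colour agree, so neither gives a contrast between matching and mismatching stimuli.

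**4. Size**

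Let I be the extra time on mismatched trials when players respond to print colour, and f × I the extra time when they respond to the word. If caffeine removes a share c of the interference, the measurable effects are c × I and c × f × I. Their ratio is f, so the loss is 1 − f.

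The documents give neither f nor I. With f assumed to lie anywhere from 0 to 1, the loss runs from all to none, so the expression gives the direction (a loss whenever f is below 1) and no magnitude. The Statistics section states that six participants suffice at an alpha of 5% and power of 0.8, but it gives no effect size or standard deviation. A loss of power cannot be derived either.

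**The case against.** The strongest reply is that this is a slip of wording. The section calls the test a colour–word Stroop task, says that measures with satisfactory reliability and validity were adopted, and ties the congruent condition to the colour on screen. Players may in fact have been told to respond to print colour. This stands as a live possibility, and it is why the point is put as a wrong or inconsistent statement. It does not remove the need for correction: the incongruent definition returns to the name, and the general appeal to validated measures does not validate a different response rule.

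Three further replies stand in part:

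- The response is a learned mapping from a Chinese character to a Latin letter key, so some interference may survive under word responding.
- The protocol defines no interference score. Both trials use the same task, so a difference in speed or accuracy between caffeine and placebo remains measurable.
- The Introduction does not assign resistance to distraction to the Stroop task alone. The visual search test has its own distractors (inverted and blue letters) and does not depend on the Stroop instruction.

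A reader might infer that the task is simply word reading, that it hardly taps distraction at all, or that at least half of any interference effect is lost. The documents do not support these. They hold no interference data, and a loss of half or more appears only if f is assumed in advance to be 0.5 or less.

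**Conclusion.** The point holds in a limited form. The protocol gives one response rule for the Stroop task, and it names the word. The scoring text uses colour in one half and name in the other, and the three statements cannot be applied together. Followed literally, the task is word-directed and creates less conflict than a colour-word Stroop task, so a faster score on this part of the primary outcome is harder to read as better handling of distraction.

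The direction rests on one assumption from outside the documents: a mismatched print colour disturbs a word response less than a mismatched word disturbs a colour response. No size can be attached. The effect is confined to what the Stroop score can be taken to show. The comparison of response speed or accuracy between trials and the visual search test are untouched. The change is still worth making, because a participant instruction for a primary-outcome test belongs in the protocol and this one either misstates the task or weakens it.

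**What to change.** Four linked changes in the Outcome measure section:

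1. Instruct players to press the key for the colour in which the character is printed, ignoring its meaning.
2. Score correctness against print colour.
3. Use the same rule in the familiarization tests.
4. Define congruent trials as those where word and print colour match and incongruent trials as those where they differ, and record correctness separately within each.

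The fourth change is needed with the first. A new instruction alone gives no congruent–incongruent contrast while the conditions depend on which key was pressed. Redefining the conditions alone would leave the mismatched trials word-directed.

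If players were already told to respond to print colour, the text should be corrected to say so. If they were told to respond to the word, the Stroop result should be described as a word-directed response.

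The cost is one line of instruction, the answer key in the test script and a rewritten definition. Stimuli, keys, the 80 trials and the software stay as they are. The small downside is a slightly harder colour-to-key mapping, which the three to five familiarization tests can absorb.

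### The Stroop congruent and incongruent conditions are defined by the key pressed instead of by the stimulus, so as written the incongruent condition can contain only wrong answers

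*Protocol*

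**What the plan says.** All of the relevant text is in the Protocol; most of it is in one paragraph under Outcome measure.

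- **Stimuli.** Four colour names are shown, "presented in Chinese characters and in various colors to confuse the participants".
- **Response rule.** "The participants were required to press a key corresponding to the base color name they saw on screen".
- **Congruent.** "a congruent condition, in which the key pressed corresponded correctly to the color on screen".
- **Incongruent.** "an incongruent condition, in which the key pressed corresponded incorrectly to the color name on screen".

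The Design section ranks the outcomes: "The primary outcome was cognitive function, and the secondary outcome was shooting performance". The Stroop task and the visual search test are the two cognitive tests. The Statistics section gives the analysis: "Cognitive performance, accuracy, and hit reaction time were analyzed through a paired sample t test". No other section defines the two Stroop conditions.

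**The concern.** Because the words appear in various colours, each Stroop trial is a match or a mismatch before the participant responds. The two conditions should follow that property of the stimulus, and correctness should be a separate score. The Protocol instead uses the key pressed to assign the condition. It also changes the referent: the congruent definition looks to the colour, the incongruent one to the colour name, and the instruction is to key the name.

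An incongruent condition is meant to capture performance under interference, chiefly correct answers to mismatched words. If such answers cannot enter it, the condition measures something else.

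This also affects the treatment comparison. The Design and Statistics sections read as a paired caffeine-versus-placebo test. If the response decides which trials belong to a condition, caffeine can change the membership as well as the performance, and a within-condition difference is confounded with accuracy. If the Stroop result is a reaction time, the incongruent cell may also hold few trials.

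**Working it through.** **Inputs (Protocol, Outcome measure).** Four words, four print colours, four keys; the correct key is the colour name; the two definitions as quoted; 80 trials per test. The Participants section gives nine participants, each tested under caffeine (CAF) and placebo (PL). The Protocol states no figure on this point that could be reproduced.

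**One example.** Take the word *red* printed in blue. The instructed key is R. If the congruent definition refers to print colour, R does not match the print colour, so it is not congruent. R does match the name, so it is not incongruent either. The wrong key B meets both definitions.

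**Enumeration.** 4 × 4 × 4 = 64 combinations. Matched stimuli: 4 pairs, so 4 correct and 4 × 3 = 12 wrong keys. Mismatched stimuli: 12 pairs, so 12 correct and 12 × 3 = 36 wrong keys. Total: 16 correct, 48 wrong.

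- Reading A: congruent if key = print colour, incongruent if key ≠ word.
- Reading B: the colour on screen is taken to mean the colour name, so congruent if key = word, incongruent if key ≠ word.
- Slip reading: the colour name in the incongruent definition is a slip for the colour, so congruent if key = print colour, incongruent if key ≠ print colour.

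| Combination (correct key = word) | Reading A | Reading B | Slip reading |
|---|---|---|---|
| Matched, correct (4) | congruent | congruent | congruent |
| Mismatched, correct (12) | neither | congruent | incongruent |
| Matched, wrong (12) | incongruent | incongruent | incongruent (missorted) |
| Mismatched, wrong, key = print colour (12) | both | incongruent | congruent (missorted) |
| Mismatched, wrong, other key (24) | incongruent | incongruent | incongruent |

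Under A and B, 0 of the 12 correct keys to mismatched words are incongruent, and all 48 wrong keys are (12 + 12 + 24). Reading B reduces the labels to correct and error. The slip reading sorts all 16 correct keys properly but missorts 12 + 12 = 24 of the 48 wrong keys.

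**Other response rule.** If participants were meant to key the print colour, the definitions read as in A put the 12 correct keys to mismatched words in both conditions, and 12 wrong keys in neither.

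These are counts of logical combinations, not expected trial frequencies. The Protocol gives no split of the 80 trials by condition.

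**How full the incongruent cell would be under A or B.** The Protocol gives no error rate *e*, so 2%, 5% and 10% are assumed, with independent errors.

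- Expected incongruent trials per session = 80*e*.
- Probability that a session has none: *p* = (1 − *e*)^80.
- Probability that a participant lacks a CAF–PL pair = 1 − (1 − *p*)².
- Expected participants without a pair = 9 × that probability.

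| Assumed *e* | Trials of 80 | *p* | No pair | Of 9 |
|---|---|---|---|---|
| 2% | 1.6 | 0.1986 | 0.358 | 3.2 |
| 5% | 4 | 0.0165 | 0.033 | 0.3 |
| 10% | 8 | 0.0002 | 0.0004 | 0.0 |

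The last two columns matter only if the Stroop result is a reaction time. The Protocol does not say so; the Introduction only cites a finding that "players with experience in competitions had shorter reaction times in a Stroop test". If the result is a count, no pair is lost, but the incongruent result is then just an error count.

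**The case against.** The strongest reply is that this is a slip of description. The Protocol names a standard task run in named software and says that measures with satisfactory reliability and validity were adopted from the literature. On the slip reading every correct response is sorted properly. Only errors go astray: weighting the wrong-key combinations equally, half of them, or about 0.8, 2 or 4 of 80 trials at the assumed 2%, 5% or 10%. If only correct responses are timed, none do. The claim that no correct answer can be incongruent also depends on the word being the correct key. The missing-pair figures rest on assumed error rates and on a reaction-time measure, and they are material only at 2%. Finally, the Statistics section does not say that the Stroop result is tested by condition.

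Much of this is fair. A wording slip is plausible, harm to the analysis is possible but not shown, and the sparse-cell figures are illustrative. But the general statement about adopted measures supplies no definition of the conditions and cannot override an explicit one. The literal instruction is to key the name. Reading the rule as print colour instead does not rescue the definitions as written, because they then overlap. The slip reading itself requires a change to the text. Nor is this detail left to an analysis plan: the Protocol does give the definition, and gives it wrongly.

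**Conclusion.** The point holds, and the paragraph should be corrected. As written, with the colour name as the correct key, the incongruent condition consists only of wrong answers: 48 of 48 wrong combinations and 0 of the 12 correct answers to mismatched words. This needs no assumed error rate. It does rest on the response rule as stated; under the print-colour rule the failure is overlap instead of exclusion.

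The consequence for the caffeine comparison is conditional. If trials were sorted by response, the within-condition comparison is confounded with accuracy for one of the two tests behind the primary outcome. If scoring was conventional and only the description is wrong, the results are unaffected, but a reader cannot tell from the document which was done.

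A minor slip in the same paragraph carries no weight in this conclusion: "In each test, 80 trials lasting 5 min each were conducted". Taken literally that is 80 × 5 = 400 minutes, whereas the parallel visual search test has 80 displays in 5 minutes.

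**What to change.** Rewrite the Stroop paragraph under Outcome measure as follows:

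1. Congruent: word meaning equals print colour. Incongruent: word meaning differs from print colour.
2. State one response rule, word or print colour, as actually administered, and score every trial against it.
3. Compare caffeine with placebo within each stimulus condition, and report accuracy separately.
4. Give the actual total duration, apparently 80 trials in 5 minutes.

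Every trial then falls in exactly one condition (4 of the 16 word–colour pairs congruent, 12 incongruent), whatever key is pressed.

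The cost is one reworded paragraph. The stimulus type is set by the task, so neither a change to the task nor extra testing is needed. If trials were in fact sorted by response, the data would also have to be rescored by stimulus type.
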